Appendix 10 Global assessment of the patient disease related pain

The patient's global assessment of disease related pain will be assessed on a 0-100 mm VAS, from no pain (0 mm) to very severe pain (100 mm).

For patients <18 years of age at randomization, this question will be collected as a part of the CHAQ (see Appendix 9).

For patients ≥18 years of age at randomization, this question will be collected as a part of the SHAQ (see Appendix 9).

Appendix 11 Joint count JADAS27

The JADAS included the following 4 measures: physician global assessment of disease activity, patient/parent global assessment of well-being, active joint count and CRP.

Joint count

The JADAS27 includes the following joints: cervical spine, elbows, wrists, metacarpophalangeal joints (from first to third), proximal interphalangeal joints, hips, knees, and ankles (48).

Joint count		Left	Right
Elbow			
Wrist			
MCP	1		
	2		
	3		
PIP	1		
	2		
	3		
	4		
	5		
Knee			
Hips			
Ankles			
Cervical spine			NA
Total			

### 1 Abbreviations and definition of terms

ACR American College of Rheumatology

ADA Anti-drug antibodies

AE Adverse event

AOSD Adult-onset Still's disease

ATC Anatomical therapeutic chemical

AUClast Area under the serum concentration-time curve from time zero to

the last quantifiable concentration (Clast), calculated by the linear

up-log down trapezoidal method

AUC0-24h,ss Area under the serum concentration-time curve during a dosage

interval

CARRA The Childhood Arthritis and Rheumatology Research Alliance

CHAQ Childhood health assessment questionnaire

CL/F Apparent total clearance of drug from serum after subcutaneous

administration

CM Concomitant medication

Cmax Observed maximum serum concentration of anakinra

CRP C-reactive protein

CSR Clinical study report

DCRI Duke Clinical Research Institute

ECG Electrocardiogram

Hb Hemoglobin

ICH International council of harmonization of technical requirements

for registration of pharmaceuticals for human use

ILAR International League of Associations for Rheumatology

IL-1Ra Interleukin 1 receptor antagonist

IL-6 Interleukin 6
IL-18 Interleukin 18

IMP Investigational medicinal product

IRS Interactive response system
mITT Modified intention-to-treat

JADAS Juvenile arthritis disease activity score

LLOQ Lower limit of quantitation

MAS Macrophage activation syndrome

MedDRA Medical Dictionary for Regulatory Activities

NAb Neutralizing antibodies

NCA Non-compartmental analysis

PD Pharmacodynamics
PK Pharmacokinetics
PT Preferred term

SAE Serious adverse event
SAP Statistical analysis plan

SHAQ Stanford Health Assessment Questionnaire

SJIA Systemic juvenile idiopathic arthritis

Sobi Swedish Orphan Biovitrum

SD Standard deviation
SOC System organ class

TEAE Treatment-emergent AE

 $t_{1/2}$  Apparent terminal half-life, calculated by  $0.693/\lambda_z$ 

 $t_{max}$  Time to reach  $C_{max}$  following dose injection

VAS Visual analogue scale

Vd/F Apparent volume of distribution following subcutaneous

administration

WHO World Health Organization

#### 2 Introduction

This SAP describes the planned analysis and reporting for the Sobi anaSTILLs study (Sobi.ANAKIN-301), a randomized, double-blind, placebo-controlled, multicenter, phase 3 efficacy and safety study of 2 dose levels of subcutaneous anakinra (Kineret®) in patients with Still's disease (SJIA and AOSD).

The purpose of this SAP is to outline the planned analyses to be completed to support the CSR for protocol Sobi.ANAKIN-301. The planned analyses identified in this SAP will be included in

potential regulatory submissions and/or future manuscripts. Also, exploratory analyses not necessarily identified in this SAP may be performed to support the clinical development program. Any post-hoc, or unplanned, analyses not identified in this SAP will be clearly identified in the CSR.

The structure and content of this SAP provides sufficient detail to meet the requirements identified by the FDA and ICH: Guidance on statistical principles in clinical trials (ICHE9). All work planned and reported for this SAP will follow internationally accepted guidelines, published by the American Statistical Association and the Royal Statistical Society, for statistical practice.

# 3 Study objectives and endpoints

### 3.1 Primary objective

The primary objective of this study is:

• To demonstrate efficacy of anakinra versus placebo in Still's disease as assessed by ACR30 response including absence of fever.

# 3.2 Secondary objectives

The key secondary objective is:

• To demonstrate early onset of efficacy of anakinra versus placebo in Still's disease.

The secondary efficacy objectives are:

- To evaluate sustained efficacy of anakinra versus placebo in patients that reached at least ACR30 response at Week 2.
- To evaluate efficacy of anakinra versus placebo during 12 weeks treatment.
- To evaluate time to study drug discontinuation in anakinra versus placebo.
- To evaluate glucocorticoid tapering in anakinra and placebo treated patients.
- To evaluate the efficacy of anakinra in the 2 separate dose groups.

The safety objective is:

• To evaluate the safety of anakinra.

The pharmacokinetic objective is:

• To evaluate the PK of anakinra.

The immunogenicity objectives are:

- To evaluate occurrence of ADAs, NAbs and cross-reactivity.
- To evaluate ADAs in relation to safety.
- To evaluate ADAs, and NAbs in relation to efficacy.

The productivity objective is:

• To evaluate absenteeism from school or work.

The exploratory objectives are:

- To explore PK/PD relationship between IL-1Ra/anakinra serum concentrations and selected efficacy and safety parameters.
- To explore the PK properties of anakinra using population analysis.
- To explore the effect of anakinra on the exploratory inflammatory biomarkers (IL-6, IL-18, calprotectin and neopterin) in the treatment of patients with Still's disease.
- To collect a blood sample for future analysis for genetic factors potentially contributing to the patient's response to anakinra, safety and tolerability. Will be reported separately.

### 3.3 Study endpoints

### 3.3.1 Primary efficacy endpoint

The primary efficacy endpoint is:

• ACR30 response at Week 2 with absence of fever attributable to the disease during the 7 days preceding Week 2.

**Definition of ACR30 response:** An improvement of  $\geq 30\%$  from baseline in at least 3 of any 6 variables listed below. Also, no more than 1 of the 6 variables may worsen by  $\geq 30\%$  from baseline.

- 1. Physician global assessment of disease activity (VAS)
- 2. Patient/parent global assessment of overall well-being (VAS)
- 3. Number of joints with active arthritis
- 4. Number of joints with limitation of motion
- 5. Assessment of physical function (CHAQ/SHAQ)
- 6. CRP (mg/L)

**Definition of fever:** Body temperature  $\geq 38.0$  °C (100.4 °F) attributable to the disease

### 3.3.2 Secondary endpoints supporting the primary objective

The secondary endpoints supporting the primary objective are:

- ACR30 response at Week 1 with absence of fever attributable to the disease during 24 hours preceding Week 1.
- ACR50, ACR70 and ACR90 response at Week 1 and Week 2 with absence of fever attributable to the disease during 24 hours before Week 1 and 7 days preceding Week 2.
- Response in the **individual components** of ACR at Week 1 and Week 2. Response is defined as an improvement of > 30%, 50%, 70% and 90% from baseline.
  - o Physician global assessment of disease activity (VAS)

- o Patient/parent global assessment of overall well-being (VAS)
- o Number of joints with active arthritis
- o Number of joints with limitation of motion
- Assessment of physical function (CHAQ/SHAQ)
- o CRP (mg/L)
- Absence of fever during the 7 days preceding Week 2.

#### 3.3.3 Key secondary efficacy endpoints

The key secondary efficacy endpoints are:

- Absence of fever during the 24 hours preceding Week 1.
- Change from baseline in physician global assessment of disease activity (VAS) at Week
- Change from baseline in patient/parent global assessment of overall well-being (VAS) at Week 1.
- Change from baseline in CRP at Week 1.

#### 3.3.4 Other secondary efficacy endpoints

Other secondary efficacy endpoints are:

- Sustained ACR response at Week 4, Week 8 and Week 12 compared to ACR response at Week 2.
- ACR30, ACR50, ACR70 or ACR90 response with absence of fever 24 hours before Week 1 or during the 7 days preceding the visit at Week 2, Week 4, Week 8 and Week
- Absence of rash 24 hours before Week 1 or during the 7 days preceding Week 2, Week 4, Week 8 and Week 12.
- Change from baseline in CRP, Hb, platelet count and ferritin at Week 1, Week 2, Week 4, Week 8 and Week 12.
- Change from baseline in patient/parent global assessment of disease related pain (VAS) at Week 1, Week 2, Week 4, Week 8 and Week 12.
- Inactive disease at Week 12.
- Change from baseline in JADAS27 at Week 2 and Week 12.
- Time to study drug discontinuation for any reason.
- Time to study drug discontinuation due to lack of efficacy or progressive disease.
- Number of patients who have initiated tapering of glucocorticoids at Week 12.
- Number of patients with decreased dose of glucocorticoids by at least 50% at Week 12 compared to baseline.
- Percentage decrease of glucocorticoid dose at Week 12 compared to baseline.
- Efficacy endpoints as described above, of anakinra in the 2 separate dose groups.

### 3.3.5 Safety endpoints

The study has the following safety endpoints:

• AEs (including MAS), vital signs and laboratory safety assessments.

### 3.3.6 Pharmacokinetic endpoints

The study has the following PK endpoints:

• Anakinra trough plasma concentrations and repeated-dose PK parameters at Week 12.

### 3.3.7 Immunogenicity endpoints

The study has the following immunogenicity endpoints:

- Occurrence of ADAs, NAbs, and cross-reactivity and titer levels of ADA and NAbs at baseline, Week 1, Week 2, Week 4, Week 8 and Week 12.
- Occurrence and titer levels of ADAs in relation to AEs at Week 1, Week 2, Week 4, Week 8 and Week 12.
- Occurrence and titer levels of ADA, including NAb in relation to ACR response and CRP at Week 1, Week 2, Week 4, Week 8 and Week 12.

# 3.3.8 Productivity endpoints

The study has the following productivity endpoints:

• Number of days off school or work due to Still's disease.

#### 3.3.9 Exploratory endpoints

The study has the following exploratory endpoints:

- Population PK/PD parameter estimates and associated covariates describing intra- and inter-individual variability in respective parameter estimate.
- Population PK parameter estimates and associated covariates describing intra-and interindividual variability in respective parameter estimate.
- Change from baseline in exploratory inflammatory biomarkers at Week 1, Week 2 and Week 12.

If the investigator judges that a patient must discontinue study drug before the Week 12 visit, a Study Drug Discontinuation visit should be performed before standard of care treatment is initiated, if possible. If the study drug is discontinued on a scheduled visit, the Study Drug Discontinuation visit should be performed instead of the scheduled visit unless the study drug is discontinued at the Week 12 visit. For a patient that discontinues study drug before the Week 2 visit, the Week 2 visit should still be performed according to the original schedule of assessments. However, if the Study Drug Discontinuation visit is performed within 3 days prior to the Week 2 visit, the scheduled Week 2 visit should be omitted. A final follow-up call will be conducted 4 weeks after the last IMP administration according to the assessments described for the Week  $16_{Tel}$  visit in the protocol.

All patients included in the study will be carefully monitored by the investigator and if there is a need, patients can withdraw from the study at any time.

If a patient is on glucocorticoid treatment the dose can be tapered starting earliest at the Week 2 visit. The patient must have reached at least ACR50 response with no fever in the preceding 7 days at the visit initiating tapering.

If a patient develops MAS, the patient will terminate the study drug and will be treated according to standard of care. If the MAS event occurs before the Week 2 visit it is preferred, if possible, that the patient returns to conduct the Week 2 visit according to the schedule of assessments. For all patients that are diagnosed with MAS, irrespective of timepoint in the study, a follow-up call should be conducted 4 weeks after the last IMP administration according to the assessments described for the Week  $16_{\text{Tel}}$  visit before the patient is withdrawn from the study. MAS is defined as an event of special interest in this study and must be reported as an SAE.

Once all patients have conducted the Week 16Tel (End of Study) visit or their last visit in case of early discontinuation, data cleaning activities will be completed and the database will be locked before the final analysis will be conducted.

# 4.2 Selection of study population

A total of 81 patients was originally planned to be randomized, but fewer patients are expected since recruitment will be stopped earlier. At least 12 patients are expected to be randomized, with a 2:1 allocation (anakinra:placebo).

For inclusion into the study, a patient should have active Still's disease, diagnosed not more than 6 months prior to randomization. Diagnosis of Still's disease:

- a) If < 16 years of age at disease onset, according to adapted ILAR criteria i.e., CARRAcriteria for SJIA.
- b) If  $\geq 16$  years of age at disease onset, according to Yamaguchi criteria.

# 4.3 Method of treatment assignment and randomization

The different treatment groups are;

- placebo (corresponding volume of anakinra 2 mg/kg/day [max 100 mg/day]), or
- placebo (corresponding volume of anakinra 4 mg/kg/day [max 200 mg/day]), or
- anakinra 2 mg/kg/day (max 100 mg/day) or
- anakinra 4 mg/kg/day (max 200 mg/day)

The ratio between the treatment groups is 1:1:2:2, i.e. the ratio placebo:anakinra is 1:2.

The randomization numbers are generated in blocks. Each block includes the four treatment groups per the ratio described above. The block size will not be revealed before breaking of the blind.

The randomization is stratified by age at onset of disease (< 16 years,  $\ge$  16 years) and glucocorticoid use at inclusion (yes, no). The original plan was to randomize 81 patients with the requirement to randomize at least a third of the patients with an age at onset of disease < 16 years and a third of the patients with an age at onset  $\ge$  16 years, however this is no longer a requisite due to early stopping of the study. Medidata balance randomization and trial supply system is used for IRS and Biostatistics at DCRI is responsible for generating the randomization scheme, which will link sequential patient randomization numbers to treatment codes.

# 5 Sequence of planned analysis

### 5.1 Interim analyses

There is no planned interim analysis for this study.

# 5.2 Analyses and reporting

All final analyses identified in the SAP will be performed after the last patient has completed the study. The SAP will be finalized, locked and signed prior to database lock and subsequently the breaking of blind.

Any post-hoc analyses included in the CSR, which were not identified in this SAP, will be clearly identified as such in the relevant section of the CSR.

# **6** Sample size determination

Assuming the ACR30 response rate with absence of fever at Week 2 is 65 % in patients receiving anakinra and 25 % in placebo patients, 81 evaluable patients (54 anakinra and 27 placebo) would be required to ensure 90 % power in demonstrating that anakinra improves clinical features of Still's disease using a two-sided test at a 5 % significance level. These assumptions are based on the canakinumab and tocilizumab phase 3 clinical studies in SJIA where 65 to 85 % of active patients and 10 to 25 % of placebo patients responded at two weeks,

as well as the Nordstrom study in AOSD where 50 % of anakinra treated patients were in remission after 4 weeks of treatment (Nordstrom et al 2012).

Since recruitment will be stopped before the planned number of evaluable patients have been included, it is anticipated that at least 12 patients will be randomized and included in the analyses.

# 7 Analysis sets

The analysis sets to be used in the statistical analyses are presented in Section 7.1 (mITT set), Section 7.2 (Safety set), and Section 7.3 (PK set).

#### 7.1 The mITT set

The mITT set is the primary analysis population and will comprise all randomized patients, except those who failed to satisfy major disease-specific entry criteria, or who received no IMP (see also section 7.4). The patients will be grouped according to randomization. The mITT is the primary analysis population for the primary and secondary efficacy endpoints.

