8.2 Definition of study populations

The following analysis sets/populations will be used for the statistical analyses:

ITT population: This population is the primary analysis population and will comprise all randomized patients, grouped according to randomization.

PP population: This population will comprise ITT patients that do not have any major protocol violations potentially influencing efficacy variables up to the Week 2 visit. Patients will be grouped according to treatment actually received and the correct stratification information.

Safety population: This population will comprise all patients who received at least one kit of investigational product and patients will be grouped according to the actual treatment received. Patients randomized to placebo that incorrectly received one kit of anakinra or more will be included in the corresponding anakinra group. Patients randomized to anakinra who incorrectly received only placebo kits will be included in the placebo group.

PK population: This population will comprise patients who received anakinra without any major protocol deviations with respect to administration of investigational product. All patients with at least one PK measurement will be included in the population to present anakinra plasma concentrations. Patients in the repeated dose PK population should not have any major protocol deviations with respect to the repeated dose PK measurements.

The ITT is the primary analysis population for the primary and secondary efficacy endpoints. The PP population will be used as a sensitivity analysis for the primary endpoint, the endpoints supporting the primary objective and the key secondary endpoints. The Safety population will be used for the safety analyses. The PK population will be used for evaluating the PK of anakinra.

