#### 7.4 Protocol deviations

Protocol deviations related to study inclusion or exclusion criteria, conduct of the study, patient management or patient assessment will be reviewed prior to DBL and described in the CSR as appropriate.

Major protocol deviations that will lead to exclusion from the mITT analysis set are the following:

- Patient failed to satisfy major disease-specific entry criteria in accordance with the adapted ILAR or Yamaguchi criteria, as detailed in the CSP.
- Patient did not get any dose of IMP.

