### 8.2 Handling of missing data and outliers

#### 8.2.1 Imputation for efficacy endpoints

For all endpoints related to the primary objective the following imputation will be used:

- Patients that discontinue study drug prior to Week 2 will be set to non-responders.
- For patients with missing information in any of the ACR30 components, that specific component will be set to no change. For patients with missing information on fever, the patients will be treated as having a presence of fever.

For the key secondary endpoints the following imputation will be used:

- Patients who have missing information on fever during 24 hours preceding Week 1 will be treated as having a presence of fever in the analysis.
- For the other secondary endpoints no imputation will be performed, i.e., all presentations will be based on observed data.

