### 8.4 Multiple comparisons and multiplicity

A fixed sequential testing will be used in the sense that the key secondary efficacy endpoints will only be tested if the null hypothesis related to the primary efficacy endpoint is rejected. No further adjustments will be applied. Testing of all secondary efficacy endpoints will be exploratory.

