### 12 Efficacy analyses

### 12.1 Primary efficacy endpoint

The primary endpoint, ACR30 response at Week 2 with absence of fever attributable to the disease during the 7 days preceding Week 2, will be analyzed using the mITT analysis set and will use no missing data imputation other than that described in 8.2.1. Patients who have discontinued study drug prior to Week 2 will be treated as non-responders in the analysis.

The null and alternative hypotheses with respect to the primary efficacy endpoint are defined as:

 $H_0$ :  $P_{anakinra} = P_{placebo}$  $H_A$ :  $P_{anakinra} \neq P_{placebo}$ 

where P is the proportion of patients with ACR30 response as defined for the primary endpoint. Fisher's exact test will be used to test the hypothesis at the two-sided significance level of  $\alpha$ =0.05. The proportion of patients with ACR30 response in each treatment group and the difference in response rates between anakinra and placebo with the corresponding 95 % exact (Santner-Snell) confidence interval (Santner et al 1980) will be presented.

A patient listing of ACR response and the response for individual components by visit, with information on dose of anakinra, age at onset of disease and glucocorticoid use at inclusion, will be provided.

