### 12.1.1 Sensitivity analyses of the primary endpoint

As a sensitivity analysis for both the primary analysis of ACR30 (+ absence of fever) at Week 2 and the supportive analysis of ACR30 (+ absence of fever) at Week 1 a comparison of treatment groups including the actual response data for patients who have discontinued study drug will be performed using the ACR assessment closest to Week 2 or Week 1 respectively. However, patients with study drug discontinuation due to progressive disease will still be treated as non-responders as in the main analysis. The same exact methods as for the primary analysis will be used.

If the analysis of the primary efficacy endpoint results in a statistically significant outcome a tipping point analysis will be performed. The number of responders that can potentially be observed among patients with a missing ACR30 outcome at Week 2 (e.g. when non-response is assigned in the primary analysis due to discontinuation of study drug) in the anakinra group versus the placebo group will be presented in a basic tipping point display. Pairs of number of responders in the anakinra and placebo group that lead to statistical significance will be marked

and pairs that lead to non-significance will not be marked. The tipping point boundary is the staircase region between marked and unmarked rectangles (Yan et al 2009).

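### The SAP replaces the protocol's all-randomised primary efficacy set with an mITT set and plans no efficacy analysis on all randomised patients

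*SAP*

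**What the plan says.** Protocol 8.2, on the ITT population: "This population is the primary analysis population and will comprise all randomized patients, grouped according to randomization". It uses that population for the primary and secondary efficacy endpoints and adds a per-protocol set for sensitivity.

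SAP 7.1 gives the same role to an mITT set, which keeps patients in their randomised groups but takes all of them "except those who failed to satisfy major disease-specific entry criteria, or who received no IMP". SAP 7.4 repeats the two grounds for exclusion. One is receiving no dose of IMP. The other reads "Patient failed to satisfy major disease-specific entry criteria in accordance with the adapted ILAR or Yamaguchi criteria, as detailed in the CSP".

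SAP 7 lists three sets only: mITT, Safety and PK. Under SAP 12.1 the primary endpoint "will be analyzed using the mITT analysis set". SAP 12.1.1 has two sensitivity analyses. In the first, "a comparison of treatment groups including the actual response data for patients who have discontinued study drug will be performed", using the assessment closest to the visit. The second is a tipping-point display for missing Week 2 outcomes, done only if the primary result is significant. SAP 12.2 and 12.3 name no further set.

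The SAP attributes its other reductions (sample size, stratification, subgroups) to early stopping or small numbers. It gives no reason for replacing the ITT population.

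**The concern.** Both exclusions act after randomisation, so the primary comparison is no longer guaranteed to be the randomised one. In a trial of 81 patients, one or two exclusions would seldom matter. With about 12 they can decide the primary test, and under SAP 8.4 "the key secondary efficacy endpoints will only be tested if the null hypothesis related to the primary efficacy endpoint is rejected".

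The diagnostic exclusion is the more important of the two, because it may not be independent of what happens later. Protocol 4.1 says that no diagnostic test exists and that the disease can resemble infection or malignancy. In Protocol Appendix 1 the Yamaguchi criteria exclude infections and malignancies and apply only where nothing else explains the picture. The adapted ILAR criteria exclude patients with IgM rheumatoid factor found twice, at least 3 months apart. Such facts can come to light during follow-up, perhaps because a patient failed to respond. SAP 7.4 requires review before database lock, but does not say the judgement is confined to what was known at entry.

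If a patient is excluded, no planned analysis shows whether the conclusion depends on it. The patient listing in SAP 12.1 might allow a reader to redo the test, but the SAP does not say that excluded patients will be listed.

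**Working it through.** **The plan's own figure.** Inputs from Protocol 8.1 and SAP 6: 65 % v 25 %, two-sided 5 %, 90 % power, 2:1. The pooled rate is (0.25 + 2 × 0.65)/3 = 0.517. The uncorrected placebo size is

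[1.96 √(1.5 × 0.517 × 0.483) + 1.282 √(0.25 × 0.75 + 0.65 × 0.35/2)]² / 0.40² = 22.6, so 23.

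With the continuity correction it is (22.6/4) × [1 + √(1 + 6/(22.6 × 2 × 0.40))]² = 26.2, so 27. That gives 27 + 54 = 81, as stated. The sample size is not in question.

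**Size actually expected.** SAP 4.2 expects at least 12 patients at 2:1. I take 8:4, and 12:6 as a larger case; both splits are assumptions.

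**Single tables.** With the margins fixed, a table with a/n responders on anakinra and b/m on placebo has probability C(n,a) C(m,b) / C(n+m, a+b). The two-sided Fisher p sums all tables no more probable than the one observed.

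| All randomised | p | One patient excluded | p |
|---|---|---|---|
| 6/8 v 0/4 | (28 + 28)/924 = 0.061 | 6/7 v 0/4 (anakinra non-responder) | 7/462 = 0.015 |
| 7/8 v 1/4 | (32 + 1)/495 = 0.067 | 7/7 v 1/4 (anakinra non-responder) | 4/165 = 0.024 |
| 8/8 v 1/4 | 4/220 = 0.018 | 8/8 v 1/3 (placebo non-responder) | 3/55 = 0.055 |

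Not every table flips: 7/8 v 0/4 gives 0.010 and 7/7 v 0/4 gives 0.003.

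**How often.** I enumerated every table with binomial weights, removed one patient and recomputed p. The rates are the SAP 6 planning values (65/25) and the most favourable ends of the ranges it cites (85/10). Entries are the percentage of trials in which significance is gained / lost, given exactly one exclusion.

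| Split, rates | Power before exclusion | Random patient | Random non-responder |
|---|---|---|---|
| 8:4, 65/25 | 6.7 % | 2.3 / 0.3 | 4.2 / 1.3 |
| 8:4, 85/10 | 51 % | 4.5 / 2.0 | 8.0 / 7.9 |
| 12:6, 65/25 | 27.7 % | 4.3 / 2.2 | 6.1 / 5.3 |
| 12:6, 85/10 | 89.6 % | 1.4 / 2.4 | 2.2 / 6.4 |

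The last column is the adverse case, in which exclusion is linked to a poor outcome.

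**Type I error.** The maximum over equal response rates from 0.01 to 0.99 is 0.68 % at 8:4 and 1.07 % after one random exclusion. At 12:6 it is 2.74 % before and at most 3.67 % after. All are below 5 %.

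**Never-dosed patient.** SAP 8.2.1 says "Patients that discontinue study drug prior to Week 2 will be set to non-responders". It also sets missing components to no change and missing fever to fever present. It does not cover a patient who was never dosed but has complete Week 2 data. At 8:4 with one such anakinra patient, the mITT result is 6/7 v 0/4, p = 0.015. On all randomised patients it is 6/8 v 0/4, p = 0.061, if that patient counts as a non-responder. It is 7/8 v 0/4, p = 8/792 = 0.010, if an observed response is used.

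**The case against.** The best case for the SAP is that this will rarely matter.

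- **Never-dosed patients should be rare.** Protocol 6.5.1.2 and Appendix 5 put randomisation and the first dose at the same Day 1 visit, and Protocol 6.4.3.1 has staff supervise that dose. This stands. A never-dosed patient with complete Week 2 data is rarer still; without such data SAP 8.2.1 already gives non-response.
- **The exclusions are narrow, pre-specified and judged blind.** Deviations are reviewed before database lock, the SAP is signed before unblinding, and patients stay grouped as randomised. This stands and makes deliberate bias unlikely. It does not make a diagnostic exclusion independent of a patient's course, so the adverse-case column cannot be dismissed, although nothing in the rule itself selects non-responders.
- **The flip rates assume an exclusion.** They do, and the documents give no probability for one. SAP 6 expects at least 12 patients to be both randomised and analysed. If the chance of one exclusion were 10 % (an assumption), random-exclusion flips at 8:4 would occur in 0.10 × (2.33 + 0.34) = 0.27 % to 0.10 × (4.47 + 1.99) = 0.65 % of trials.
- **The gate matters little.** At 65/25 and 8:4 it opens 6.7 % of the time, and SAP 8.4 calls secondary testing exploratory. This stands at those rates, but at 85/10 power is 51 %.
- **An exclusion would be visible.** SAP 9 reports the numbers randomised and in the mITT set. A reader would learn that someone was excluded, but not what the test gives with that patient included.

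These points limit how often the gap matters. They do not supply the missing analysis.

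**Conclusion.** The concern holds. The SAP departs from the protocol's primary efficacy set without giving a reason and specifies no efficacy analysis that restores an excluded patient. At about 12 patients, one exclusion can move the primary p-value across 0.05 in either direction. Given one exclusion, the chance of a change is a few per cent if the patient is random. In the adverse case it reaches about 16 % (8.0 + 7.9) at 8:4 and 85/10.

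This rests on assumed 8:4 and 12:6 splits, response rates taken from SAP 6, and exactly one exclusion. If nobody is excluded there is no effect. The finding is about showing robustness, not about inflated type I error. The change should be made, but it is not a fatal flaw.

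**What to change.** In SAP 12.1.1, add the primary Fisher test and Santner-Snell interval on all randomised patients, grouped as randomised (the Protocol 8.2 population), as a sensitivity analysis. State that patients who received no IMP count as non-responders in it. The mITT set can remain primary.

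An optional clarification in SAP 7.4: the diagnostic exclusion refers to status at entry, judged on information available before the first dose.

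The cost is one table and one sentence; if no patient is excluded, the table simply repeats the primary result. The downside is that a misdiagnosed patient stays in the all-randomised run and may dilute the effect slightly, which is acceptable in a sensitivity analysis.
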